Official Title:	Alignment and Comfort Assessments using Non-Sliding Lingual Orthodontic Technique (BRIUS) and Conventional Bracket Systems
NCT number:	NCT04347018
Document Type:	Study Protocol and Statistical Analysis Plan
Date of the Document:	08/17/2022

Study Design

This is a non-blinded single-center randomized clinical controlled pilot trial of growing orthodontic patients who underwent comprehensive multi-arch fixed orthodontic treatment for the first time. Subjects were randomized into one of two groups: BR lingual appliance (experimental intervention group) and LFFA (standard intervention group). The study was reviewed and approved by institutional review boards at the University at Buffalo Health Sciences (IRB # 00004055 - Appendix1). The study was also registered on the ClinicalTrials.gov Protocol Registration and Results System (ID# NCT04347018).

The patients were assessed for leveling and aligning by comparing their initial presentation prior to bonding (T1) with their alignment 18 weeks after bonding (T4).

Sample Population

Sample population included growing patients between 10 and 18 years of age, with full permanent dentition, and presented for orthodontic treatment at the University at Buffalo School of Dental Medicine (UBSDM) orthodontic clinic. Subjects were randomly allocated into one of two groups: BR and a LFFA group.

Participant Selection Criteria

The sample inclusion criteria were:

- Female and male 10 to 18 years old
- Mild to moderate case difficulty, defined by American Board of Orthodontics Discrepancy Index (DI) of 0 to 20
- Angle's Class I and Class II (up to half cusp) molar and canine relationship.
- Fully erupted permanent dentition (excluding third molars).
- Mild to moderate crowding (7 mm or less).
- Good oral hygiene, determined by the orthodontist at each adjustment visit.
- Undergoing treatment with fixed orthodontic appliances in both jaws for a minimum of 6 months.

The exclusion criteria were:

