Subjects were excluded if they had transposed, impacted, or missing teeth, previous history of orthodontic or orthognathic surgical treatments, treatments that involved tooth extractions or orthognathic surgery, systemic illness or craniofacial syndrome or disorder, missing appointments, and compromised oral hygiene. Subjects who had radiographic bone loss observed on the dental panoramic image were excluded. Additionally, any drugs that affect tooth movement used prior to the beginning of, or during the study would also exclude the subject.

Sample size

Sample size was calculated based on the results of Scott et al.³⁴ that determined a standardized difference of 0.98 in the rate of tooth alignment within a period of 34 days would give a clinically relevant difference of 0.8 mm between two groups. For statistical power of 80% at a significance level of 0.05, 17 subjects were needed in each group for a total sample size of 34 subjects.

Study time points

Total observation duration for all study participants was 18 weeks from the first day of bonding maxillary and mandibular arches, which were both bonded on the same appointment.

Periodic records included intra-oral photos and an intra-oral scan for all subjects at the records appointment (T1), at 6 weeks – first adjustment visit (T2), at 12 weeks second adjustment (T3) and at 18 weeks third adjustment (T4). During each visit, in addition to the periodic records including intra-oral photos and scans, any broken brackets were repositioned for both groups.

Outcome Measures

There were two outcomes measured in this study, the effectiveness of tooth movement and patient comfort at 6, 12 and 18 weeks after appliance bonding.

A] Effectiveness of tooth movement:

1. Alleviation of crowding: Little's Irregularity Index (LII) which measures the alignment discrepancy in the five contact points of the lower anterior region was assessed between T1 and T4 for every patient. The scores were measured digitally by identifying the center of the mesial (CoM) and distal (CoD) contact points on each tooth at the same vertical level. The 3D slicer software was used to measure the horizontal distance between CoM and CoD of adjacent teeth in millimeters. The scores were then compared between the two groups (BR and LFFA) and comparisons were made in the different timepoints within each group.

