2. Changes in 3D individual tooth positions: To assess the extent of movements achieved in all three planes for each maxillary and mandibular tooth from 6-6, digital model superimpositions were performed using 3D Slicer software (www.slicer.org Harvard University, Boston, MA, USA). Maxillary superimpositions were done based on the method described by Aliaga et al.³⁵ using the palatal rugae. Mandibular superimposition was completed by overlaying the pre- and post-treatment digital models on the mucogingival junction which is a stable and reliable landmark according to a study by Ioshida et al.

B] Patient comfort level

Data obtained from the perceived comfort questionnaires was evaluated by identifying chronological pattern of any pain experienced as well as any other patterns according to the data obtained. The extent of comfort will be described by a percent at each time point, two-sample independent t-test will be done to compare the pain between the two groups.

Comfort level was assessed using an electronic survey instrument developed by Wu et al.³⁷ (Appendix 2). This valid and reliable instrument used a VAS score to assess the overall comfort, comfort in the tongue, cheeks, lips, gingiva, and face and jaw.³⁸ It also asked about the use of medications. The survey instrument was sent online to patients through QuestionPro (Austin, TX, USA). Each patient was instructed to complete and submit the survey daily, on the first seven days after their first visit (T1), second visit (T2), third visit (T3) and fourth visit (T4).

Procedure of the study

Subject Randomization

Prior to initiating sample recruitment, block randomization was carried out by a statistician who was not involved in recruiting or treating patients. Results of the randomization, whether BR or LFFA were written down on 34 different sheets of paper. Each sheet was then individually enclosed in opaque sequentially numbered envelopes. An envelope corresponding to the number of the sample joining the study would be opened to find out which group the new sample would fall into.

Subject recruitment process

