All tooth movement data were assessed for normality with the Shapiro-Wilks test. Sample sizes were relatively small in both the BR and FFA groups, so the power of this test to correctly identify non-normal distributions is likely low. Therefore, t-tests for differences between groups were performed where appropriate along with the Mann-Whitney nonparametric tests. The difference in between group continuous questionnaire outcomes and continuous demographic data were also evaluated for significance with the Mann-Whitney test. The within group tests for the paired differences in T1 and T4 values of Little's Irregularity Index were done with the Wilcoxon signed rank test. Categorical questionnaire outcome and categorical demographics data associations with the BR and FFA groups were tested for independence using Fisher's exact test, since there were instances of low (< 5) or and zero cell counts. A post hoc power to sample size analysis using Little's Irregularity Index data was also performed under an assumption of normality. The estimated effect size used was determined by first calculating the mean of the paired T1 to T4 differences in both the BR and FFA groups, and then taking the difference between these group means. The standard deviation for the sample size calculations was taken as the pooled value of the standard deviations of both groups' paired differences. All statistical analysis was performed using R (v4.0.4) through RStudio (v.461).

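### The between-arm comparison of Little's Irregularity Index uses only unadjusted tests, does not state which contrast is tested, and never uses the baseline value as a covariate

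*Combined protocol and SAP*

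**What the plan says.** The Statistical Analysis section gives one between-arm method for tooth-movement data: "t-tests for differences between groups were performed where appropriate along with the Mann-Whitney nonparametric tests". LII is the first item under effectiveness of tooth movement in Outcome Measures, so this sentence is taken to cover it. The term where appropriate is not defined. No regression, ANCOVA, mixed model or covariate appears in the document.

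Outcome Measures says that LII "was assessed between T1 and T4 for every patient", so a baseline value exists for each participant. On the comparison it says: "The scores were then compared between the two groups (BR and LFFA) and comparisons were made in the different timepoints within each group". The Statistical Analysis section names the paired T1-T4 difference in two other places: the within-group Wilcoxon test and the post hoc power calculation ("The estimated effect size used was determined by first calculating the mean of the paired T1 to T4 differences"). It does not name it for the between-arm test.

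Four facts about the design bear on this:
- Study Design calls the trial a pilot.
- Participant Selection Criteria admit any crowding up to 7 mm.
- Subject Randomization describes block randomisation and mentions no stratification on crowding.
- The Sample size section states that "17 subjects were needed in each group for a total sample size of 34 subjects".

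**The concern.** Initial irregularity can vary widely under these entry criteria, and nothing in the allocation balances it. With 17 per arm, some chance imbalance in T1 LII is likely. A comparison of T4 scores ignores T1. A comparison of change subtracts T1 in full, which fixes its slope at 1 whatever the true relation between T1 and T4. ANCOVA estimates that slope from the data.

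At stake are the width of the confidence interval and the power of the LII comparison. A reader also cannot tell which quantity the reported p-value concerns. ANCOVA removes that ambiguity: once T1 is in the model, the estimated arm difference is the same whether the outcome is T4 LII or T1-T4 change, apart from sign.

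**Working it through.** **1. The plan's own figure.** Inputs from the Sample size section: standardised difference 0.98, 80% power, significance level 0.05 (two-sided assumed). n per arm = 2(1.960 + 0.842)²/0.98² = 16.3, rounded up to 17, as stated. An exact t calculation gives 17.36, and power at 17 per arm is 79.1%. The sample size is not in dispute.

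**2. The only spread figure available.** The same section says the standardised difference "would give a clinically relevant difference of 0.8 mm between two groups". The implied SD is 0.8/0.98 = 0.816 mm. The section ties these figures to a rate of alignment over 34 days, not to LII at 18 weeks. Using them here is therefore an assumption, and all power figures below are illustrative.

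**3. Chance imbalance in T1.** The standard error of the T1 difference between arms is √(2/17) = 0.343 SD. The probability of an imbalance above 0.3 SD in either direction is about 38% (0.3/0.343 = 0.87). Above 0.5 SD it is about 14% (0.5/0.343 = 1.46).

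**4. Formulas.** Let k be the T4/T1 SD ratio (assumed 0.5 or 1) and r the T1-T4 correlation (assumed 0.3 to 0.8).
- SD of T4 = k × SD of T1.
- SD of change = SD of T1 × √(1 + k² − 2rk).
- Residual SD under ANCOVA = SD of T4 × √(1 − r²).
- Power is from the noncentral t distribution, with 32 df for the unadjusted tests and 31 for ANCOVA. ANCOVA power is averaged over chance T1 imbalance.

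**5. One case in full: k = 1, r = 0.5.** T4 and change both have SD 0.816. Noncentrality is 0.98/0.343 = 2.86 and power is 79%. For ANCOVA the residual SD is 0.816 × √0.75 = 0.707, noncentrality is 0.8/(0.707 × 0.343) = 3.30 and power is 88%.

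**6. All cases, power (%) for 0.8 mm with 17 per arm, shown as T4 scores / change / ANCOVA.**

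| | r 0.3 | r 0.5 | r 0.7 | r 0.8 |
|---|---|---|---|---|
| 0.816 is the change SD, k = 1 | 91 / 79 / 92 | 79 / 79 / 88 | 57 / 79 / 84 | 42 / 79 / 82 |
| 0.816 is the change SD, k = 0.5 | >99 / 79 / >99 | >99 / 79 / >99 | 98 / 79 / >99 | 96 / 79 / >99 |
| 0.816 is the T4 SD, k = 1 | 79 / 65 / 81 | 79 / 79 / 88 | 79 / 95 / 97 | 79 / 99 / >99 |
| 0.816 is the T4 SD, k = 0.5 | 79 / 30 / 81 | 79 / 36 / 88 | 79 / 46 / 97 | 79 / 54 / >99 |

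With 0.816 as the change SD, ANCOVA gains about 3 to 21 points over change and about 0 to 9 over the better unadjusted metric. With 0.816 as the T4 SD, it gains about 0 to 20 points over the better unadjusted metric.

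**7. Where the gain disappears.** If r = 0 and T4 scores have 79% power, ANCOVA has about 78%, a loss of 1 to 2 points. The break-even correlation against T4 scores is approximately √(1 − (2.0369/2.0395)²/(1 + 1/31)) = 0.18, where 2.0369 and 2.0395 are the two-sided 5% t values on 32 and 31 df.

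Power of the Mann-Whitney test was not calculated.

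**The case against.** The strongest reply is that nothing is invalid. Randomisation makes the unadjusted comparison unbiased, the trial is a pilot, and the gain rests on a correlation and SDs that the documents do not give. All of that stands. A reader might infer that the planned tests are biased, and the documents do not support that.

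A second reply is that the contrast is nearly stated, since the within-group test and the post hoc effect size both use paired T1-T4 differences. This stands in part. Change is the likelier reading, and T1 would then enter by subtraction, so it would be wrong to say that the baseline goes unused. Subtraction is still not covariate adjustment, and the between-arm test itself is never tied to change.

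Third, much larger gains can be produced by assuming a T1 SD of 1.5 to 2.0 mm, loosely suggested by the 7 mm crowding limit. A reader might infer gains over change of up to 57 points that way. Crowding is not LII, and those assumptions put the change SD at 0.95 mm or more, above the plan's only figure. The large gains over change in the last row of the table have a similar weakness: they need a T1 SD of twice 0.816 mm.

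Fourth, ANCOVA's lead in every cell partly reflects a grid that starts at r = 0.3. That is right, and the break-even shows where the lead ends.

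Finally, a reader might infer that ANCOVA should now become the main analysis. The Statistical Analysis section does not allow that. Its post hoc power calculation already used each group's LII differences, so outcomes had been seen.

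**Conclusion.** The point holds as a matter of precision and clarity. The plan compares LII between arms with unadjusted tests, leaves the contrast unstated, and makes no covariate use of a baseline measured on every patient.

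The direction of the gain is dependable for correlations clearly above about 0.18. Its size is not: it runs from nearly nothing to about 20 points over the better unadjusted metric. This rests on an SD of 0.816 mm carried over from a 34-day alignment rate, a 0.8 mm difference carried over in the same way, SD ratios of 0.5 or 1, correlations of 0.3 to 0.8, and normally distributed data.

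The point does not extend to the 3D tooth positions. Under Step 5 of the superimposition methods these are already T1-to-T4 distances, with no baseline value to adjust for.

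**What to change.** 1. State which LII contrast the reported t-test and Mann-Whitney test used: T4 scores or T1-T4 change.
2. Add an ANCOVA of T4 LII on arm with T1 LII as covariate, reported as an adjusted mean difference with 95% confidence interval. Label it post hoc and supplementary, and show it beside the existing unadjusted results without replacing them.
3. In any version or follow-on trial planned before data are seen, make this ANCOVA the main LII analysis, with one rank-based test as a labelled sensitivity analysis that names its contrast.
4. Leave the 3D displacement analysis as it is.

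The cost is a few sentences and one re-analysis of data already held, with no new measurement. One degree of freedom is spent. The model assumes a roughly linear relation of T4 to T1. In simulations with LII bounded at zero and spread rising with baseline, its type I error was 4.6% to 4.9%, so the bound is not a serious obstacle.

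### Alignment is analysed by significance tests only; the between-arm difference in irregularity change should be reported with a 95% confidence interval in place of post hoc power

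*Combined protocol and SAP*

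**What the plan says.** The Statistical Analysis section sets out the alignment analysis as a list of tests. Between groups, "t-tests for differences between groups were performed where appropriate along with the Mann-Whitney nonparametric tests". Within groups, the T1 and T4 values of Little's "Irregularity Index were done with the Wilcoxon signed rank test". No confidence interval is named anywhere in the document.

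Under Outcome Measures, the entry on alleviation of crowding plans a comparison of LII scores between BR and LFFA, and adds that "comparisons were made in the different timepoints within each group".

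The Statistical Analysis section also computes each arm's mean T1 to T4 change in LII and the difference between the two means. For the spread, "The standard deviation for the sample size calculations was taken as the pooled value of the standard deviations of both groups' paired differences". The only stated use of these quantities is a post hoc power and sample size analysis.

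The Sample size section starts from a "standardized difference of 0.98 in the rate of tooth alignment within a period of 34 days", which "would give a clinically relevant difference of 0.8 mm between two groups". With power set at 80% and the significance level at 0.05, it concludes that "17 subjects were needed in each group for a total sample size of 34 subjects".

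**The concern.** A small randomized pilot mainly yields an estimate and a measure of its precision. This plan produces the estimate and its SD but stops at p-values and a power figure. A p-value above 0.05 can come from a trial that rules out a difference worth caring about, or from one that leaves such a difference open. Only the interval separates the two cases.

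Post hoc power does not fill the gap. When it is computed from the observed difference and the observed SD, its noncentrality is difference / (SD × √(2/n)), which is the t statistic itself. It therefore restates the p-value on another scale.

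The within-arm tests do not fill it either. Each compares an arm with its own baseline. Two significant within-arm results, or one significant and one not, do not establish how BR compares with LFFA.

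At stake is whether readers of a null result can tell what it excludes.

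**Working it through.** **Inputs.** From the Sample size section: difference 0.8 mm, standardized difference 0.98, 80% power, significance level 0.05, 17 per arm. The SD of the 18-week change is not given. The implied value is 0.8 / 0.98 = 0.816 mm, which comes from a 34-day rate. Its use at 18 weeks is an assumption, so it is varied up to 2.0 mm.

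**Reproducing the plan's figure.** n per arm = 2 × ((1.960 + 0.842) / 0.98)² = 16.35, rounded up to 17. This matches the plan. It is a two-sided calculation (one-sided gives 13). With the exact t-test, power at 17 per arm is 79.1%, close to the stated 80%.

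**Half-width of the 95% CI for the between-arm difference.** Half-width = t(0.975, 2n − 2) × SD × √(2/n). With n = 17: 2.037 × 0.816 × 0.343 = 0.570 mm.

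**What a non-significant result leaves open.** Non-significance means an absolute observed difference below the half-width. The far limit of the interval can then reach 2 × 0.570 = 1.14 mm. To exclude 0.8 mm in both directions, the observed difference must be below 0.8 − 0.570 = 0.230 mm.

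**Example.** For an observed 0.30 mm, t = 0.30 / (0.816 × 0.343) = 1.07 and p = 0.29. The interval is 0.30 ± 0.57, or −0.27 to 0.87 mm, so it is not significant and does not exclude 0.8 mm.

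**Range over the unknown SD, 17 per arm (SD taken as the observed value):**

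| SD of change (mm) | Half-width (mm) | Farthest limit if non-significant (mm) | Excludes 0.8 mm if observed difference is below |
|---|---|---|---|
| 0.816 (implied) | 0.57 | 1.14 | 0.23 mm |
| 1.0 (assumed) | 0.70 | 1.40 | 0.10 mm |
| 1.25 (assumed) | 0.87 | 1.75 | not possible |
| 1.5 (assumed) | 1.05 | 2.10 | not possible |
| 2.0 (assumed) | 1.40 | 2.79 | not possible |

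The change-over is at an SD of 0.8 / (2.037 × 0.343) = about 1.15 mm. If losses left 15 or 12 per arm (assumed), the half-width at SD 0.816 mm would be 0.61 or 0.69 mm.

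**How often it matters (200,000 simulated trials, normal data, SD 0.816 mm, 17 per arm).** A trial counts as inconclusive if it is non-significant and its interval includes 0.8 or −0.8 mm.

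- True difference 0: about 37% inconclusive. 95% of trials are non-significant, and about 61.5% of those do exclude 0.8 mm in both directions.
- True difference 0.4 mm: about 45% inconclusive.
- True difference 0.8 mm: about 21% non-significant, and about 18% inconclusive.

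With an assumed SD of 1.25 mm, only about 3% of non-significant trials exclude 0.8 mm when the true difference is 0, and 56% of trials with a true 0.8 mm difference are non-significant.

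**The case against.** The strongest reply is that the plan is better than a list of p-values suggests, and several stronger readings that a reader might infer are not supported.

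- **That the appliances are compared only through within-arm tests.** Outcome Measures plans a between-group comparison of LII, and the t-test and Mann-Whitney test are specified for tooth movement data generally. The within-arm tests are an addition, and nothing in the document uses them to compare BR with LFFA.
- **That no between-arm estimate exists.** The difference in mean change and a pooled SD are both computed. What is missing is the interval, and any use of the estimate beyond post hoc power.
- **That a non-significant result cannot exclude 0.8 mm.** At the implied SD it does so whenever the observed difference is below about 0.23 mm, which is most non-significant trials if there is no true difference.
- **That the plan equates non-significance with similarity.** No section says so. It is a risk in reading the results and not a stated rule.
- **That 0.8 mm is an equivalence margin.** It sized a comparison looking for a difference over 34 days, and no equivalence aim is stated. A rule declaring similarity within ±0.8 mm at 18 weeks would be a new design choice and is not proposed here.

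All five replies stand. A sixth, that a pilot need not report precision, does not: precision is a main product of a pilot. If the post hoc calculation was meant to help size a later trial, the pooled SD it needs can be reported beside the interval.

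**Conclusion.** The point holds in a limited form. Alignment is analysed by significance tests only. The quantities needed for an interval are already computed, but go into a post hoc power analysis that cannot show which differences the data exclude.

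At the plan's own inputs a non-significant result may leave 0.8 mm open, and whether it does depends on the observed difference and SD. The 0.57 mm half-width and the percentages that follow from it rest on 17 analysed per arm, approximate normality, and a 34-day SD carried over to 18 weeks. The document supports none of these for the 18-week change. A larger SD or smaller arms would widen the interval. The 0.8 mm serves here only as a yardstick borrowed from the sample size calculation. The case for reporting the interval does not depend on it.

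**What to change.** In the Statistical Analysis section:

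1. Report the BR minus LFFA difference in T1 to T4 LII change with its 95% CI, in place of the post hoc power analysis.
2. Beside the Mann-Whitney test, report the Hodges-Lehmann shift with its 95% CI.
3. State that a non-significant result will not be described as similarity without reference to that interval.
4. Treat the within-arm T1 to T4 tests as descriptive, and draw no comparison of appliances from them.

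The cost is a few sentences of text and standard R output. No new data are needed, and because the section is written in the past tense this can be done as a change in reporting. The downside is that a null result may have to be reported as inconclusive.

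### No deciding test is named for between-group tooth movement, so the 5% level is not guaranteed; separately, two sections name different tests for comfort.

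*Combined protocol and SAP*

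**What the plan says.** The Statistical Analysis section applies a Shapiro-Wilk test to all tooth-movement data, then discounts it at this sample size because "the power of this test to correctly identify non-normal distributions is likely low". From that it concludes that "t-tests for differences between groups were performed where appropriate along with the Mann-Whitney nonparametric tests". Outcome Measures places Little's Irregularity Index (LII) and the 3D tooth positions together under effectiveness of tooth movement, so the sentence covers both.

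For comfort, Outcome Measures part B says that a "two-sample independent t-test will be done to compare the pain between the two groups". The Statistical Analysis section says instead: "The difference in between group continuous questionnaire outcomes and continuous demographic data were also evaluated for significance with the Mann-Whitney test".

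Other analyses have a single named test: Wilcoxon signed rank for the within-group LII change, Fisher's exact test for categorical data, and Mann-Whitney for continuous demographic data.

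The Sample size section works from a "standardized difference of 0.98 in the rate of tooth alignment within a period of 34 days" and concludes: "For statistical power of 80% at a significance level of 0.05, 17 subjects were needed in each group".

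**The concern.** Two tests of the same group comparison give two p-values. Once the normality test has been set aside as a way of choosing between them, nothing in the text takes its place: the condition for using a t-test is undefined, neither test is labelled primary, and there is no rule for a split result. A report could rest on whichever p-value is below 0.05, and the chance of a false positive would then exceed that of either test alone. The LII comparison is the most exposed, because the sample-size calculation concerns tooth alignment.

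The comfort problem is of a different kind. Two sections give different instructions for VAS data from the same questionnaire, and a reader cannot tell which test the comfort conclusion rests on.

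**Working it through.** **Inputs.** From the Sample size section: standardised difference 0.98, significance level 0.05 (sidedness not stated), power 80%, 17 per group. From the Statistical Analysis section: t-test and Mann-Whitney for between-group tooth movement. The documents give no outcome distributions, so the data shapes below are assumptions.

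**Step 1: reproduce the plan's sample size.** With n per group = 2(z₀.₉₇₅ + z₀.₈₀)² / d²:

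2 × (1.960 + 0.842)² / 0.98² = 2 × 7.849 / 0.9604 = 16.3, rounded up to 17.

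This matches the plan. A one-sided calculation gives 13, so the plan's figure is two-sided. An exact t-test calculation gives 17.4, so 18; t-test power at 17 is 79.1%. The sample size was thus set on the scale of a difference in means.

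**Step 2: error per comparison when there is no group difference.** 200,000 simulated trials per data shape, 17 per group, pooled t-test and exact Mann-Whitney, each two-sided at 0.05:

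| Assumed shape | t-test | Mann-Whitney | Either significant | Both significant | Tests disagree |
|---|---|---|---|---|---|
| Normal | 5.00% | 4.92% | 5.95% | 3.97% | 1.98% |
| Exponential | 4.57% | 4.80% | 6.38% | 2.98% | 3.40% |
| Lognormal | 3.73% | 4.82% | 6.26% | 2.29% | 3.97% |
| t with 3 df | 4.46% | 4.90% | 6.13% | 3.23% | 2.90% |

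Check on the normal row: either = 5.00 + 4.92 − 3.97 = 5.95%.

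The simulation standard error is about √(0.0638 × 0.9362 / 200,000) = 0.05 percentage points, so about 6.0% to 6.5% is a fair range for the either-test rule. Independent tests would give 1 − 0.95² = 9.75%; these two are strongly correlated, so the true figure is much lower. At an assumed 10 per group, the either-test rate is 5.4% to 5.7%.

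**Step 3: the comfort passages side by side.** Outcome Measures part B: t-test for pain, in the future tense. Statistical Analysis: Mann-Whitney for continuous questionnaire outcomes, in the past tense. The instrument is scored on a VAS, so both sentences cover the same kind of data. No sentence says that one replaces the other, and none says that both tests are run on comfort data. The rates in Step 2 therefore do not carry over to comfort.

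**Step 4: set this beside multiplicity.** First molar to first molar in both arches is 24 teeth, and Step 5 of the superimposition method yields four measures per tooth (x, y, z and the 3D vector): 24 × 4 = 96 possible comparisons. At 5% each, 96 × 0.05 = 4.8 false positives are expected with no true differences. Under the either-test rule the figure is 96 × 0.0595 = 5.7 to 96 × 0.0638 = 6.1. Naming one test removes the excess of about 0.9 to 1.3 and leaves the 4.8.

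**The case against.** The best defence is that the two tests are a robustness display. The section gives its reason (a normality test has little power here), and the sentence can be read as Mann-Whitney throughout with t-tests added. On that reading only a label is missing. No passage says that either result may be claimed, and if both had to be significant the error would be 2.3% to 4.0%, which is conservative. The excess under the either-test rule is only about 1.0 to 1.5 points, the trial calls itself a pilot, and multiplicity is the larger threat. All of this stands. It limits the size of the point but does not supply the missing rule.

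A reader might infer three stronger things that the documents do not support:

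- That the 5% level is breached. This needs an either-test rule, which is nowhere stated; the level is not guaranteed, and no more can be said.
- That every comparison in the trial is affected. Within-group LII, demographic and categorical analyses each have one named test.
- That the comfort conflict inflates the error rate. The t-test sentence may be leftover planning text, and nothing shows two competing p-values for comfort.

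It can also be said that preferring a mean-based analysis is a matter of taste, since either test alone stays at about 5% or less. That is true of error control. The mean scale is preferred because the trial was sized on it, and because the post hoc power analysis also uses a difference in means with a pooled standard deviation.

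**Conclusion.** The point holds in a limited form. For between-group tooth movement (LII and per-tooth distances) the plan names two tests and no deciding one. If either result may be claimed, the error per comparison is about 6.0% to 6.5% at 17 per group, against about 5% or less for one named test. In 2.0% to 4.0% of trials with no true difference the tests disagree, and the plan has no rule for those. These figures rest on the planned group size, the four assumed data shapes and two-sided testing at 0.05.

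The contradiction on the comfort test is established by the text alone and needs no simulation. Both are modest problems in a pilot, but they bear on how the main comparisons are decided and are cheap to correct.

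**What to change.** 1. **LII.** Make one between-group analysis decisive: a linear model for T4 LII with treatment group and T1 LII as terms, reporting the adjusted mean difference with its confidence interval. It uses data already collected and stays on the scale of the sample-size calculation. This model is not in the current plan.
2. **Per-tooth distances.** Name one deciding between-group test and remove the undefined condition on the t-test.
3. **Mann-Whitney for tooth movement.** Where it is not the deciding test, report it as a labelled sensitivity analysis that cannot change the conclusion.
4. **Comfort.** Make Outcome Measures part B and the Statistical Analysis section name the same test.
5. **Timing.** The Statistical Analysis section is written in the past tense, so a choice before analysis may no longer be possible. In that case, declare the choice as post hoc and show both p-values.

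The cost is a few sentences, one extra model term for LII, and the loss of the option to quote the more favourable p-value. The fix does not address multiplicity across the per-tooth comparisons, which needs its own remedy.
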